6.5 Prior Therapy

Eligible subjects will need to have had a documented history of inadequate response to a ≥ 1 -month treatment with topical medication, such as corticosteroids (class I to V), calcineurin inhibitors, and/or topical PDE4 inhibitor (e.g., crisaborole). Medical history is sufficient but the medication and duration of treatment should be documented. Inadequate response should also be documented to have occurred within 6 months prior to the Screening visit. Additionally, subjects for whom topical treatments are considered medically inadvisable will be considered to have satisfied the requirements related to prior therapy.

6.6 Concomitant Therapy

6.6.1 Permitted Therapies

6.6.1.1 Emollients

Subjects must apply a basic, non-medicated emollient of their choice (except those containing urea) on their skin, including on AD lesions, at least twice a day. The emollient use must be initiated at least 7 days prior to Day 1 and subjects must continue using it at the same frequency (at least twice daily) throughout the study. However, on the day of scheduled visits, subjects should refrain from emollient use for at least 8 hours prior to each clinic visit.

Every effort should be made to use the same emollient throughout the study for the same body region. However, the chosen emollient may differ depending on the body region (e.g., body vs face emollient may be different). The commercial name of the selected emollient(s) will be recorded in the source document and the eCRF. No other products may be applied to the lesions during the study.

6.6.2 Prior Use of Dupilumab, Tralokinumab, or an Oral JAK Inhibitor

Prior use of dupilumab, tralokinumab, or an oral JAK inhibitor for the treatment of atopic dermatitis will be assessed at screening. Per the eligibility criteria, subjects with a history of dupilumab, tralokinumab, or an oral JAK inhibitor will be allowed in the study provided that they have achieved the relevant washout period and a history of a clinical response. This clinical response may be assessed by interview of the subject by the PI. Enrollment of dupilumab- or tralokinumab-exposed subjects will be capped at approximately 20% and randomization will be stratified by prior use.

6.6.2.1 Skin Care

Use of sunscreen products and protective apparel are permitted when sun exposure cannot be avoided.

Regular skin care (e.g., cleansing and bathing) is permitted during the study. New skin care regimens that are not present at baseline (e.g., bleach baths) should not be introduced through the course of the study.

6.6.2.2 Anti-infectives

Topical and systemic anti-infective medications are permitted during the study, independent of the location of the infection, should the Principal Investigator identify an acute infection requiring treatment.

6.6.2.3 Anti-histamines

Non-sedating anti-histamines (e.g., loratadine, cetirizine, or fexofenadine) are permissible. Sedating anti-histamines (e.g., doxepin, diphenhydramine) are permissible so long as these medications were on a stable dosing regimen within 7 days prior to the Baseline (Day 1) visit and remain on the stable dosing regimen through the duration of the treatment period (Day 113). Dose adjustments must be discussed with the Investigator prior to change.

6.6.2.4 Medications for Conditions Unrelated to AD

Subjects who are taking oral medications for conditions unrelated to AD should be on a stable dosing regimen within the 7 days prior to the Baseline (Day 1) visit. Adjustments to the regimen may be made after the Baseline visit if medically necessary. If a new medication is required to treat an emerging condition, these are allowable, provided the medication is not among the prohibited therapies. New concomitant medications should be discussed with the Medical Monitor prior to initiation.

6.6.2.5 Corticosteroids for Nose, Lungs, Eyes, and/or Ears

Intranasal corticosteroids and inhaled corticosteroids are allowed. Eye and ear drops containing corticosteroids are also allowed when used as directed.

6.6.2.6 *Herbals and supplements*

Subjects may take herbals and/or supplements with the following conditions. First, subjects taking herbals and/or supplements at screening who wish to discontinue these may do so provided that they do the following for the duration of the study: 1) continue to refrain from taking the herbal/supplement and 2) do not introduce a new herbal and/or supplement. Second, subjects who intend to continue taking herbal products or supplements during the trial must agree to continue the regimen documented at Screening throughout the study unless discontinuation is considered medically necessary.

6.6.3 **Prohibited Therapies or Procedures**

Female subject agrees not to have egg retrieval during the study and for 30 days after the last study drug administration.

Male subject agrees not to donate sperm during the study and for 90 days after the last study drug administration.

Table 3 lists prohibited medications that are not to be used from the defined washout periods before the first administration of study treatment at the Day 1 visit through the last study visit.

Subjects who start prohibited medications or therapies as a treatment for AD or other reasons during the study may be withdrawn from study treatment for safety reasons. If in any doubt, Investigators are advised to discuss medications with the Medical Monitor.

Table 3 Prohibited Therapies or Procedures for Study Duration with Washout Periods

Prohibited Medications, Products, and Procedures	Washout Period Prior to First Dose (Day 1)
Cell-depleting agent (e.g., rituximab)	6 months
Any marketed or investigational biological therapeutic (other than dupilumab)	16 weeks or 5 half-lives (whichever is longer)
Dupilumab	12 weeks
Oral investigational drugs	8 weeks or 5 half-lives of the investigational drug (whichever is longer)
Major elective surgical procedures	8 weeks
Systemic JAK inhibitors	8 weeks
Parenteral antibiotic	4 weeks
Live-attenuated vaccine (including but not limited to adenovirus-based COVID-19 vaccines such as the Janssen COVID-19 vaccine)	4 weeks
mRNA-based COVID-19 vaccines (Pfizer-BioNTech or Moderna)**	2 weeks
Allergen-specific immunotherapy regimen (Note: subjects may continue on a stable dose of allergen immunotherapy if achieved 4 weeks prior to the Day 1 visit)	4 weeks
Systemic immunosuppressive/immunomodulating drugs (other than biologics) (e.g., methotrexate, cyclosporine A), immunoglobulins, blood products, and/or systemic corticosteroids (e.g., oral, intravenous, intraarticular, rectal)	4 weeks
Tanning beds or phototherapy (NBUVB, UV-B, UVA1, or PUVA)	4 weeks
Systemic antibiotics	2 weeks (oral) 4 weeks (parenteral)
Topical corticosteroids as these medications could affect AD*	2 weeks
Additional topical medicated treatment that could affect AD including, but not limited to phosphodiesterase 4 (PDE4) inhibitors, JAK inhibitors, calcineurin inhibitors, tars, antimicrobials, and medical devices.	2 weeks
Topical product containing urea	1 week
Topical antibiotics	1 week
Medicated emollient (regulated as medical device)	1 week

Abbreviations: AD=atopic dermatitis; COVID-19=coronavirus disease 2019; JAK=Janus kinase;

NBUVB=narrowband ultraviolet-B; PDE4=phosphodiesterase 4; PUVA=psoralen-UV-A; UVA1=ultraviolet A1; UV-B=ultraviolet B.

*Please also refer to [Section 6.6.4](#) regarding rescue medications for AD.

**mRNA-based COVID-19 vaccines (or boosters) are allowed after the end of the treatment period. See also refer to [Section 8.9.2](#) for additional guidance.

6.6.4 Rescue Medications

Subjects who require topical corticosteroids, calcineurin inhibitors, or PDE4 inhibitor medications that could directly impact AD disease activity prior to Day 57 will be withdrawn from study drug and the study if requiring such topical therapies prior to Day 57.

Starting at Day 57, rescue medications for persistent, intolerable AD activity may be considered by the Investigator. Investigators must document evidence of continued active AD with EASI unchanged from or greater than the Baseline EASI score over 2 consecutive visits before initiating therapy. All subjects requiring rescue therapy between Day 57 (Week 8) and Day 113 (Week 16) will remain in the study and on study drug until Week 16.

After the end of treatment at Day 113 and during the follow-up phase, subjects may also initiate rescue if either the subject or investigator feels that there is persistent, intolerable AD activity.

Permitted rescue medications include low- to moderate-potency (class IV-class VII) topical corticosteroids ([Appendix 14](#)) and should be applied only to problem areas. A topical calcineurin inhibitor, topical PDE4 inhibitor (e.g., crisaborole), or low-potency topical steroid may be used on the face if affected. Subjects who require rescue therapy will be considered non-responders for all efficacy endpoints with data imputed for subsequent continuous endpoints for all time points as detailed in the Statistical Analysis Plan (SAP). Ideally, the specified medication for rescue treatment would be supplied by the clinic so that the tube could be weighed prior to administration. In addition, use of the specified medication should be recorded in the e-Diary, and the medication should be brought to clinic at subsequent visits to assess amount of medication used.

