9.4.5 Missing Data

For the primary and key secondary efficacy endpoints, the efficacy data collected after the start of rescue medication will be set to missing. All missing data up to Week 16 will be imputed using a multiple imputation (MI) technique as follows:

- Intermittent missing data will first be imputed using the Markov Chain Monte Carlo (MCMC) method implemented with the SAS PROC MI procedure and imputed datasets with monotone missing pattern will be generated. This applies to intermittent missing data prior to the intercurrent events including early termination of the study treatment as well as initiation of rescue medications.
- The monotone missing values will then be imputed with the imputation model estimated from subjects in the placebo group using the SAS PROC MI procedure with MNAR statement. This approach is based on the missing not at random (MNAR) assumption. This assumes that the missing data in

the RPT193 doses post treatment discontinuation and/or the start of rescue medication follow similar profile as the placebo group.

- Response status (Yes, No) will be derived from the imputed scores in each MI datasets for binary endpoints. The results of the multiple MI datasets will then be combined into a single analysis using PROC MIANALYZE.

As a sensitivity analysis, all missing continuous data up to Week 16 will also be imputed by using last observation carried forward (LOCF). Missing data for responder endpoints will be imputed as treatment failures (TF). Additional sensitivity analyses under different assumptions for missing data handling may be explored in the SAP.

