### A. Estimand

The main estimands associated with the primary and key secondary endpoints to support regulatory decisions are described in the following table:

Attribute	Description
Treatment	RPT 193-02 (50mg, 200mg, 400mg) and Placebo
Population	Adult subjects with moderate-to-severe AD as defined by the inclusion/exclusion criteria
Endpoint	
Primary Endpoint
 
 
% change in Eczema Area Severity Index (EASI) from baseline at Week 16
 
 
Key Secondary Endpoints
 
 
% of subjects achieving a Validated Investigator Global Assessment (vIGA) score of 0 or 1 at Week 16
 
% of subjects achieving EASI-75, defined as a 75% reduction in EASI from baseline to Week 16
 
% change from baseline in PP-NRS from an itch daily e-Diary at Week 16.
 

Intercurrent Events	
 
Early termination of study treatment: Subjects who discontinue from the study treatment prior to Week 16 will be analyzed by the treatment policy strategy, i.e., all data collected after termination of study treatment but prior to rescue medication will be included in the analysis. Missing post discontinuation values will be imputed according to details provided below.
 
Use of rescue medications: Subjects who use rescue medication during the 16-week treatment period will be analyzed by the hypothetical strategy. All EASI/vIGA/PP-NRS scores collected after the start of rescue medication will be set to missing. The missing data after the use of rescue medication will be imputed to follow a similar profile as the placebo group.
 

Population-level Summary	
Primary Endpoint
 
 
Difference in mean percent change from baseline in EASI score between each RPT193 dose and placebo at Week 16.
 
 
Key Secondary Endpoints
 
 
Difference in percentage of subject achieving vIGA of 0 or 1 between each RPT193 dose and placebo at Week 16.
 
Difference in percentage of subject achieving EASI-75 between each RPT193 dose and placebo at Week 16.
 
Difference in mean percent change from baseline in PP-NRS
 

	between each RPT193 dose and placebo at Week 16.
--	--

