## 2. Missing EASI, vIGA and PP-NRS

Missing data will be imputed for the primary and secondary endpoints, which includes the composite EASI score, vIGA and PP-NRS for the 16-week treatment period. Assessment after the use of rescue will be set to missing prior to any imputation. No imputation is planned for the follow-up period. The following missing data techniques will be utilized:

**Last Observation Carried Forward (LOCF):** All missing data up to Week 16 will be imputed by the last observed value carried forward for any subsequent missing values. For patients with only baseline value, the baseline value will be carried forward to Week 16. This will be applied to the continuous endpoints of composite EASI score and PP-NRS.

**Worst Observation Carried Forward (WOCF):** All missing data up to Week 16 will be imputed by the worst observed value carried forward for any subsequent missing values. For patients with only baseline value, the baseline value will be carried forward to Week 16. This will be applied to the continuous endpoints of composite EASI score and PP-

NRS.

**Treatment Failures (TF):** All missing binary endpoint data up to Week 16 will be imputed as failure. This will be applied to key secondary binary endpoints of EASI-75, responder and vIGA score of 1 or 0, and other secondary endpoints of EASI-50, EASI-90, at least 2-point reduction in vIGA, at least 3-point/4-point reduction PP-NRS.

**Observed Cases (OC):** No missing data will be imputed. All observed data will be included. To reiterate, data after the rescue medication will be set to missing.

**Multiple Imputation (MI) under MAR:** Missing continuous endpoints of EASI, and PP-NRS will be imputed using the multiple imputation (MI) with analysis of covariance (ANCOVA) model as the primary analysis for time-points at which no value is observed. MI will be performed under missing at random (MAR) assumption. The MI is a simulation-based approach where missing values are replaced by multiple Bayesian draws from the conditional distribution of missing data given the observed data and covariates, creating multiple completed data sets.

For the EASI assessment, all missing scheduled visits as outlined in the protocol will be imputed. For the PP-NRS assessment, all missing weekly visits will be imputed.

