#### **Control-based PMM-MI procedures for EASI, PP-NRS, and vIGA under MNAR**

Similar to MI under MAR, but for EASI, PP-NRS, and vIGA, data collected after the intercurrent events of rescue medication or treatment discontinuation in the RPT193 arm will be assumed missing not at random (MNAR) and resemble missing data from subjects from the placebo arm who do not discontinue treatment permanently/receive rescue medication. Imputation of missing data at Week 16 will be done using a control-based Pattern Mixture Model Multiple Imputation (PMM-IM) where missing data in the study drug (RPT-193) arm as well as the placebo arm will be imputed from observed data in the placebo arm.

The intermittent missing data will be imputed separately for each treatment group using the Markov Chain Monte Carlo (MCMC) method implemented with the SAS PROC MI procedure. 100 imputed datasets will be generated.

For each of the 100 datasets a monotone missing data pattern will be achieved. The monotone missing values will then be imputed from subjects in the placebo group using the SAS PROC MI procedure with MNAR statement. This assumes that the missing data will follow a similar profile as the placebo group.

After the completion of the imputation, the assessments collected after the discontinuation of study treatment yet before to the use of rescue medication will be restored. The example code can be found in Appendix II.

The categorical secondary endpoints will be derived from the imputed scores in each MI datasets.

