## **D. Secondary Efficacy Analyses**

### **1. Key Secondary Efficacy Analysis**

The key secondary analysis will be based on the FAS and will use control-based PMM-MI for both categorical and continuous endpoints to handle missing data. The key secondary analysis endpoints are as following:

- Percent of subjects achieving a vIGA score of 0 or 1 at Week 16. Analyzed as a binary

endpoint.

- Percent of subjects achieving EASI-75, defined as a 75% reduction in EASI from baseline to Week 16. Analyzed as a binary endpoint.
- Percentage change from baseline in PP-NRS from an itch daily e-Diary at Week 16. Analyzed as a continuous endpoint.

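### The plan gives two rules for rescued subjects in responder endpoints: Protocol 6.6.4 makes them non-responders, while Protocol 9.4.5 and the SAP derive EASI-75 and vIGA 0/1 from imputed scores

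*Protocol*

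**What the plan says.** Protocol 6.6.4 (Rescue Medications) separates two kinds of endpoint: "Subjects who require rescue therapy will be considered non-responders for all efficacy endpoints with data imputed for subsequent continuous endpoints for all time points". Imputation is mentioned only for continuous endpoints, with detail left to the SAP. From Day 57, rescue requires documented "EASI unchanged from or greater than the Baseline EASI score over 2 consecutive visits before initiating therapy".

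Protocol 9.4.5 (Missing Data) covers the primary and key secondary endpoints together. Efficacy data after rescue become missing and are multiply imputed from a placebo-based model. Then: "Response status (Yes, No) will be derived from the imputed scores in each MI datasets for binary endpoints".

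The SAP follows 9.4.5:
- Estimand table (II.A), one rescue row for continuous and binary endpoints alike: "All EASI/vIGA/PP-NRS scores collected after the start of rescue medication will be set to missing", and "The missing data after the use of rescue medication will be imputed to follow a similar profile as the placebo group".
- Control-based PMM-MI text (IV.D.2): "The categorical secondary endpoints will be derived from the imputed scores in each MI datasets".
- Key secondary analysis (VI.D.1): it "will use control-based PMM-MI for both categorical and continuous endpoints to handle missing data". The table in VI.B confirms this as the main analysis of vIGA 0/1 and EASI-75.
- Treatment failure (TF, IV.D.2): "All missing binary endpoint data up to Week 16 will be imputed as failure". For the key secondary endpoints it is a sensitivity analysis only (VI.B, VI.D.1).

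Two further places bear on the rule. For the other secondary responder endpoints, the VI.B table makes MI under MAR the main method and TF a sensitivity method, while the text of VI.D.2 uses TF for categorical endpoints. The time-to-response endpoints in VI.D.2 censor a rescued subject at the last assessment before rescue.

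**The concern.** A programmer working from Protocol 6.6.4 and one working from Protocol 9.4.5 or the SAP would report different main results for EASI-75 and vIGA 0/1. Under 6.6.4 a rescued subject has probability 0 of being a responder. Under the analysis sections that probability is above 0, although rescue from Day 57 is open only to subjects whose EASI has stayed at or above baseline at two visits running. Neither the SAP text nor the example code in Appendix II resets these subjects to non-response after imputation.

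At stake is what the key secondary responder rates mean, and a distortion that follows the arm with more rescue.

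**Working it through.** **Texts side by side**

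| Endpoint | Protocol 6.6.4 | Analysis sections |
|---|---|---|
| % change in EASI, PP-NRS | imputed | imputed (agrees) |
| EASI-75, vIGA 0/1 at Week 16 | non-responder | derived from imputed score (Protocol 9.4.5; SAP II.A, IV.D.2, VI.B, VI.D.1) |
| Other secondary responders | non-responder | MI under MAR in the SAP VI.B table; TF in the VI.D.2 text |
| Time to response | non-responder | censored at rescue (SAP VI.D.2) |

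**Denominator.** The plan gives no figure for this issue. Its group size reproduces: 60 / 0.9 = 66.7, rounded up to 67; 67 × 4 = 268, as in SAP III.C.

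**Chance q that a rescued subject is imputed as EASI-75.** The documents give no EASI means, SDs, correlations or rescue rates, so these are assumptions: placebo mean change m of −30% to −45%, SD s of 35 to 45, between-visit correlation ρ of 0.4 to 0.8, and 0% change at the last visit before rescue. In the simplest layout (equal mean at each visit, correlation decaying by visit, k visits from last score to Week 16):

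- conditional mean = m − ρ^k × m
- conditional SD = s × √(1 − ρ^(2k))
- q = Φ[(−75 − conditional mean) / conditional SD]

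Worked cases:
- Low corner (m = −30, s = 35, ρ = 0.8, rescue at Day 85, k = 1): mean −6, SD 21, z = −69/21 = −3.29, q = 0.05%.
- Middle (m = −40, s = 40, ρ = 0.6, k = 1): mean −16, SD 32, z = −59/32 = −1.84, q = 3.3%.
- High corner (m = −45, s = 45, ρ = 0.4, rescue at Day 57, k = 2): mean −37.8, SD 44.4, z = −37.2/44.4 = −0.84, q = 20%.

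Over this grid, with different correlation structures and visit-mean paths, q runs from about 0% to 20%, with medians mostly 1% to 6%. The layout above with rescue at Day 57 is the least favourable, with a median near 8%.

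A simulation of sequential regression imputation floored at 0, as in SAP Appendix II, used assumed placebo means of −30% to −40%, SD 35 to 45 and correlation 0.6 to 0.9. Among subjects meeting the EASI condition for rescue, 0.2% to 5.4% of imputed Week 16 scores met EASI-75 and 1.8% to 16.7% met EASI-50.

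**Arm-level shift = rescue share r × q**
- Typical: 10% × 1% = 0.1 point, to 20% × 6% = 1.2 points (0.012 × 67 = 0.8 subject).
- Simulation: 10% × 0.2% = 0.02 point, to 20% × 5.4% = 1.1 points.
- Extreme: 20% × 20% = 4.0 points (0.04 × 67 = 2.7 subjects).

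**Direction.** Assume true rates of 35% active and 15% placebo, with rescue in 5% and 20%. At q = 5%: 35.25 − 16.0 = 19.25 points instead of 20. At q = 20%: 36.0 − 19.0 = 17.0 points.

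vIGA 0/1 is imputed by its own logistic model and was not computed.

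**The case against.** The strongest reply is that the SAP is faithful to the Protocol's own statistical section. Protocol 9.4.5 already derives response from imputed scores, so a reader who infers that the SAP silently overrode the Protocol goes too far, and the absence of an entry in SAP I.C is a weak complaint. This stands: the contradiction is between two Protocol sections. It does not remove the contradiction. The reference in 6.6.4 to the SAP for imputation detail does not cancel its non-responder rule.

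A reader might also infer that improvement produced by rescue medication is credited to study drug. It is not: observed post-rescue scores are discarded, and what is imputed is a no-rescue outcome under a declared hypothetical strategy. Hypothetical or composite handling is a legitimate estimand choice. What the documents cannot support is both at once.

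TF does make every subject with post-rescue data removed a non-responder, so the 6.6.4 result will be reported for the key secondary endpoints. But it is a sensitivity analysis, and it also fails everyone missing for other reasons. No planned analysis applies 6.6.4 to rescue while keeping multiple imputation for the rest.

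Nor can it be said flatly that all other responder endpoints use imputed scores, because SAP VI.B and VI.D.2 disagree. Those endpoints are described as descriptive.

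Finally, imputation conditions on the subject's own poor scores. Rescue requires EASI unchanged or worse, so assuming 0% change is the case most favourable to an imputed response. This argues for a small effect, and is accepted.

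**Conclusion.** The point holds as an unresolved contradiction affecting the main analysis of EASI-75 and vIGA 0/1. That part rests on the texts alone.

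The numerical effect on EASI-75 is modest: usually about 1 percentage point or less per arm at 10% to 20% rescue, and near 4 points only in an extreme corner. All of these sizes depend on assumed rescue rates, EASI moments and correlations. None is a firm range, and vIGA 0/1 has no estimate.

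A reader might infer that the flaw favours the drug or threatens the primary result. The documents support neither. More rescue on placebo would shrink the apparent effect under the placebo-based imputation. The primary endpoint is continuous, and 6.6.4 allows imputation there. The key secondary endpoints carry no multiplicity adjustment (SAP IV.G), although SAP II.A names them among the main estimands.

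**What to change.** Before unblinding, and so before the Week 16 efficacy analysis in SAP IV.F:

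1. In SAP IV.D.2 and VI.D.1 and in Protocol 9.4.5, state that in each imputed dataset every responder endpoint is set to non-response at visits after the start of rescue through Week 16. Keep PMM-MI for binary data missing for other reasons, and the hypothetical strategy for continuous endpoints.
2. Split the rescue row of the SAP II.A table into continuous (hypothetical) and binary (composite).
3. Reconcile the SAP VI.B table with the VI.D.2 text on the method for the other secondary responder endpoints.
4. Align the time-to-response rule with the non-responder rule, for example by treating subjects rescued before responding as not having responded through Week 16 instead of censoring them at rescue.

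If the sponsor prefers the hypothetical strategy for binary endpoints, amend Protocol 6.6.4 instead and record the choice in SAP I.C.

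The cost is wording in a few places and one derivation line after imputation, next to the step in SAP IV.D.2 that already restores off-treatment, pre-rescue scores. The downside is slightly lower responder rates, and different rescue strategies for binary and continuous endpoints, which 6.6.4 already implies.
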